## Seed based correlations

**Nuisance signal regression.** Consistent with common practice in the rs-fMRI literature, nuisance signals will be removed from the data via multiple regressions before functional connectivity analyses will be performed. This step is designed to control for the effects of physiological processes, such as fluctuations related to motion and cardiac and respiratory cycles. Specifically, each individual's 4D time series data will be regressed on nine predictors: white matter (WM), cerebrospinal fluid (CSF), the global signal, and six motion parameters. The global signal regressor will be generated by averaging across the time series of all voxels in the brain. The WM and CSF covariates will be generated by segmenting each individual's high-resolution structural image (using FAST in FSL). The resulting segmented WM and CSF images will be threshold to ensure 80% tissue type probability. These threshold masks will then be

applied to each individual's time series, and a mean time series will be calculated by averaging across time series of all voxels within each mask. The six motion parameters will be calculated in the motion-correction step during preprocessing. Movement in each of the three cardinal directions (X, Y, and Z) and rotational movement around three axes (pitch, yaw, and roll) will be included for each individual. We are aware of the potential problem that the global signal removal might cause by introducing anti-correlating artifacts. Thus we will always compare these calculations to a similar protocol where global signal will not be removed. **Seed selection.** Six 7.5-mm-radius seed regions of interest (ROIs) (containing 33 voxels) centered on the coordinates previously used by Fox et al. will be created to examine functional connectivity for each of six regions, three regions within the "task-positive" network and three within the "default mode" network. The ROIs within the task-positive network will be located in the IPS (-25, -57, 46), the middle temporal region (MT+; -45, -69, -2), and the right frontal eye field (FEF) region of the precentral sulcus (25, -13, 50). The default mode network seed ROIs will be located in the left lateral parietal cortex (LP; -45, -67, 36), medial prefrontal cortex (MPF; -1, 47, -4), and PCC (-5, -49, 40).

**Figure 2**

**Individual seed-based functional connectivity analysis.** First, each individual's residual 4D time series data will be spatially normalized by applying the previously computed transformation to the MNI152 standard space. Then the time series for each seed will be extracted from these data. Time series will be averaged across all voxels in each seed ROI. For each individual

dataset, the correlation between the time series of the seed ROI and that of each voxel in the brain will be determined. This analysis will be implemented using 3dfim+ (AFNI) to produce individual-level correlation maps of all voxels that will be positively or negatively correlated with the seed's time series (Figure 2). Finally, these individual-level correlation maps will be converted to Z-value maps using Fisher's r-to-z transformation.

### ICA-Dual regression

The dual-regression approach will be used to identify, within each subject's fMRI data set, subject-specific temporal dynamics and associated spatial maps. This involves (i) using the full set of group-ICA spatial maps in a linear model  $t$  (spatial regression) against the separate fMRI data sets, resulting in matrices describing temporal dynamics for each component and subject, and (ii) using these time-course matrices in a linear model  $t$  (temporal regression) against the associated fMRI data set to estimate subject-specific spatial maps. Finally, the different component maps are collected across subjects into single 4D images (1 per original ICA map, with the fourth dimension being subject identification) and tested voxel-wise for statistically significant differences between groups using nonparametric permutation testing (5,000 permutations). This results in spatial maps characterizing the between-subject/group differences (Figure 3).

[figure not shown]

Figure 3. Dual regression

The biggest advantage of this technique is that it will create functionally and anatomically corresponding spatial maps for every individual, thus making the patterns comparable across subjects. In traditional approaches individual ICA resulted in components where no straightforward comparison was possible.

### **Amplitude measures**

Amplitude of spontaneous low-frequency fluctuations. To examine the potentially meaningful information contained within the ALFF, two fast-Fourier transformation (FFT)-based indices, ALFF and fALFF, will be used to compute the amplitude of low-frequency fluctuations in the frequency domain. For each individual, ALFF and fALFF will be computed to identify those voxels with significantly detectable low-frequency fluctuation amplitudes. Specifically, at each voxel, ALFF is calculated as the sum of amplitudes within a specific low frequency range (0.01-0.1 Hz). fALFF is the normalized ALFF, calculated by dividing the ALFF value by the total sum of amplitudes across the entire frequency range measured in a given time series. Voxelwise ALFF and fALFF maps will be calculated for each participant in native space, and then will be transformed into the MNI152 standard brain space with 3-mm isotropic voxel size. Before statistical analyses, each individual ALFF or fALFF map will be Z-transformed (i.e., by subtracting the mean voxelwise ALFF or fALFF obtained for the individuals entire brain, and then dividing by the corresponding SD) to improve its suitability for group-level parametric analyses. The individual Z-transformed ALFF or fALFF maps will be used in subsequent group- and center-level analyses. Multiple comparisons will be corrected at the cluster level using Gaussian random field theory (min  $Z>2.3$ ; cluster significance:  $p<0.05$ , corrected).

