## Preprocessing, Overview.

All available resting-state scans were preprocessed using both AFNI (<http://afni.nimh.nih.gov/afni>) and FSL ([www.fmrib.ox.ac.uk](http://www.fmrib.ox.ac.uk)). Specific commands can be found in the preprocessing scripts that are released at [www.nitrc.org/projects/fcon\\_1000](http://www.nitrc.org/projects/fcon_1000). The first four time points of every scan will be discarded, to remove possible T1 stabilization effects, the data will be corrected for motion by aligning each volume to the mean image volume using Fourier interpolation in AFNI. Then the data will be spatially smoothed using a 6-mm FWHM Gaussian kernel. Mean-based intensity normalization will be done by scaling all volumes by the same factor (10,000).

*Seed-based correlation analyses.* The data will be temporally filtered using both a high-pass (Gaussian-weighted least squares straight-line fitting, with  $f = 100.0$  s) and low-pass (Gaussian low-pass temporal filtering, with a HWHM of 2.8 s) filter, followed by linear detrending to remove any residual drift.

*Independent component analysis-Temporal concatenation group analysis.* Consistent with common practice, temporal filtering for ICA analyses will be limited to high-pass filtering (Gaussian-weighted least squares straight-line fitting, with  $f = 100.0$  s).

*Dual regression.* This step will use the same preprocessed data as will be used in the seed-based correlation analyses.

[figure not shown]
*ALFF/fALFF.* No temporal filtering will be carried out, because the data will be examined in the frequency domain within select bands, (fALFF). Temporal despiking with a hyperbolic tangent squashing function will be performed, however, to limit extreme values. Linear trends will then be removed from the data.

*Registration and normalization.* The skull will be removed using AFNI, registration of each individual's high-resolution anatomic image to a common stereotactic space [the Montreal Neurological Institute 152-brain template (MNI152); 3 mm isotropic voxel size] will be done using a 12 degrees of freedom linear affine transformation (FLIRT). The resulting transformation will then be applied to each individual's functional dataset.

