### **Group analysis**

Our main goal in our analysis is to determine group-wise effects. The inter-subject variability however poses the main obstacle to gain meaningful effects. We will use our time-wise data to “subtract” measures between time points in the same individual, and analyze our data with repeated measure ANOVA (one factor is time point (intra-subject), other is group (inter-subject)).

Group comparison of the seed based correlation measures is straightforward, correlation values between the vmPFC and other DMN regions and subgenual cingulate will be used to detect any interaction between factors (time and group (responders and non-responders)).

The group analysis of ICA networks will be carried out by dual regression method, as it is presented on Figure 3. Individual network patterns will be obtained, and these individual patterns will be used in a second level analysis with SPM, where voxel based repeated measure ANOVA will be calculated. Similarly individual amplitude maps will be analyzed with SPM.

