### **Sample Size and Power**

The primary objective of this study is to examine and validate the differences in neuroimaging changes and network expressions across different time points during the ECT treatment. We will use repeated measure ANOVA to analyze each of the neuroimaging measures between different timepoints. Traditional power analysis in neuroimaging is challenging not only because of the inherent multiple comparisons in our studies, but also due to the fact that different voxels have different signal to noise ratio, thus effect sizes. One possible approach would be to estimate the

effect size. In order to do that, we have to estimate the distribution of the magnitude of signal change and the within subject and between subject variance. In a motor area the signal change can be well above 1%, but with cognitive or perception tests the signal is usually around 0.5-1%. According power analysis calculations with these parameter estimates it was shown that 80% power can be reached with  $N=20$  sample size.Indeed, targeting for 20 subjects in neuroimaging studies is a common practice.

**Future Studies:** MRI images and diagnostic information will be kept in an IRB-approved data repository (IRB # 06.04.089; P.I.: [name]). All study information will be kept private and identifiable information will only be released with participant permission. Participants in the current study may also be contacted about the possibility of participating in future studies.

Funding source: Brain and Behavior Research Foundation: NARSAD Young Investigator Grant

Funding source: NIMH Advanced Center for Interventions and Services Research.

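### The cluster correction for the ALFF/fALFF maps holds its stated 5% only if spatial smoothness is uniform and Gaussian, which the plan neither states nor checks

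*Combined protocol and SAP*

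**What the plan says.** Under Amplitude measures (section 13, Data Analysis), each patient's ALFF and fALFF maps are computed in native space, then "transformed into the MNI152 standard brain space with 3-mm isotropic voxel size", and standardised by the whole-brain mean and SD. The same paragraph sets the error control: "Multiple comparisons will be corrected at the cluster level using Gaussian random field theory", with a minimum Z of 2.3 and "cluster significance: $p<0.05$ , corrected".

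Under Group analysis, time points are subtracted within the individual and a repeated-measures ANOVA with time and group factors is planned. It adds: "Similarly individual amplitude maps will be analyzed with SPM". The Rationale plans three scans, one before ECT and two after.

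The Preprocessing overview says the data will be "spatially smoothed using a 6-mm FWHM Gaussian kernel". No smoothness of the final group map is given. Nor is there a check of its uniformity or autocorrelation shape, an adjustment for non-uniform smoothness, or a permutation check for the amplitude maps.

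For the ICA maps, the dual-regression section plans a voxel-wise test of group differences by "nonparametric permutation testing (5,000 permutations").

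**The concern.** A random-field cluster p-value compares the observed cluster size with the sizes expected by chance under a smoothness model. In its standard form, that model has one Gaussian smoothness for the whole search volume. The null hypothesis of interest is only that amplitude does not change. If noise is smoother in some regions, or correlated over longer distances than a Gaussian kernel implies, large chance clusters occur more often than the model expects.

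The dependence is strongest at low cluster-forming cuts. Z>2.3 is a one-sided voxel p of about 0.011, so chance clusters are many and large, and their size distribution is governed mainly by smoothness.

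An amplitude cluster reported as corrected at 0.05 would be read as an ECT effect on a network. The Benefits section says the pilot's results will guide a larger study, so poor error control here could misdirect that study.

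**Working it through.** **Inputs from the documents.** Cluster-forming cut 2.3, corrected level 0.05 and 3-mm voxels (Amplitude measures); 6-mm applied kernel (Preprocessing overview); imaging sample of about 20 (Sample Size and Power).

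**Assumed, because the documents do not give them.** Brain mask, total smoothness and smoothness pattern. The main set used an ellipsoid of V = 81,072 voxels.

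**Formula.** With u the cut and FWHM in voxels:
- resels R = V / FWHM^3
- expected clusters E = R (4 ln 2)^1.5 (2π)^-2 (u² − 1) exp(−u²/2)
- β = [Γ(2.5) E / (V p_u)]^(2/3), where p_u is the one-sided voxel p
- corrected p for a cluster of k voxels = 1 − exp(−E exp(−β k^(2/3)))
- critical size k* = [ln(E / 0.0513) / β]^1.5, where 0.0513 = −ln 0.95

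**Worked case, uniform 8 mm, u = 2.3.** FWHM = 8/3 voxels, R = 4,275, E = 152.3. V p_u = 81,072 × 0.01072 = 869.4. β = (1.3293 × 152.3 / 869.4)^(2/3) = 0.3785. k* = (7.996 / 0.3785)^1.5 = 97 voxels. The simulation, which estimated smoothness from the data, used 96.

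**The plan's own figure.** The 5% cannot be reproduced exactly without a mask and smoothness. Under the method's own assumption it holds as an upper bound: 2.5-2.9% for uniform 8-12 mm (table).

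**Why departures matter.** With a 12-mm core and an 8-mm rim, the pooled estimate is 8.9 mm and the critical size is 124 voxels. A uniformly 12-mm map would require 253. The threshold is set by an average and is too small for the smoother region.

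**Main set.** 1,000 null Z maps per scenario, one-sided, smoothness estimated from lag-1 correlation. Chance of at least one false cluster:

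| Smoothness pattern | Z>2.3 | Z>3.1 |
|---|---|---|
| Uniform 8 / 10 / 12 mm | 2.6 / 2.9 / 2.5% | 1.9 / 2.8 / 2.6% |
| Core 10, rim 8 mm | 5.3% | 2.9% |
| Core 12, rim 8 mm | 14.1% | 8.9% |
| Core 14, rim 7 mm | 41.9% | 17.7% |
| 8 mm, 10% exponential tail (12 mm) | 8.2% | 3.0% |
| 8 mm, 20% tail (12 mm) | 21.3% | 8.7% |
| 9 mm, 30% tail (15 mm) | 32.2% | 10.4% |
| 8 mm, 40% tail (12 mm) | 51.0% | 14.0% |

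The Monte Carlo standard error, sqrt(p(1−p)/1000), is 0.5 points at 2.6% and 1.6 points at 51%.

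**Small-sample set.** 150 null studies per scenario, 20 difference maps each, one-sample t at the cut equivalent to the stated Z, smoothness from residuals. The permutation column is a sign-flip test of the maximum cluster (59 flips).

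| Smoothness pattern | Random field, Z>2.3 | Random field, Z>3.1 | Permutation, Z>2.3 |
|---|---|---|---|
| Uniform 8 mm | 0% | 0% | 3.3% |
| Core 12, rim 8 mm | 14% | 4.7% | 4.0% |
| Core 14, rim 7 mm | 30% | 9.3% | 2.7% |
| 8 mm, 20% tail | 14% | 3.3% | 4.7% |

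The standard error is 2.8 points at 14% and 1.6 points at 4%.

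**Further set.** 300 null data sets, 22 maps, 67,104 voxels. Uniform smoothness gave 1.8-2.7%. A map half at 6 and half at 12 mm gave 41%; half at 8 and half at 16 mm gave 29%. Tails of 10 / 20 / 40% gave 4.5 / 14 / 41%. Permutation gave 2-6% in every scenario, and Z>3.1 with the random-field correction gave 1-18%.

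**The case against.** The strongest reply is that no excess has been shown for this trial. Every figure above 5% comes from a chosen smoothness pattern, and half a brain at twice the smoothness of the other half is a strong departure. Subtracting scans within a patient removes stable anatomical structure, which may make the noise in the difference maps more uniform than the raw maps suggest. The narrow kernel is not itself the fault: uniform 6 mm gave 1.8%. Native voxel size is not stated, so the kernel cannot be related to voxel width at the smoothing step. All of this stands. It makes the size of the problem unknown but does not supply the missing assumption or a check of it.

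The simulations also used a one-sample test on pairwise differences, whereas the plan has a repeated-measures ANOVA over three scans. That limits how far the exact percentages carry over. The reliance on the smoothness model remains.

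A reader might infer that the plan already contains the remedy and merely fails to apply it here. The dual-regression section does not go that far. It describes a voxel-wise between-group permutation test, with no mention of family-wise correction, maximum cluster size or sign-flipping.

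A reader might also double the error by citing Secondary Aim B, which counts connectivity changes in either direction. That wording concerns connectivity, not amplitude, so the figures here are kept to one direction.

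**Conclusion.** The concern holds in conditional form. The stated 5% is met, conservatively (about 0-3%), if smoothness is uniform and Gaussian. It is roughly 5-8% under mild departures and 14-50% under moderate to strong ones, for one direction, one contrast and one index. The documents do not say which case applies.

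Two stronger readings should be avoided. One is that this trial's error rate is some particular inflated figure, such as 14-41%. That range reflects selected patterns; the departures examined ran from about 4.5% to 51%. The other is that a reported cluster has that probability of being noise. Family-wise error is the chance of any false cluster when there is no effect anywhere, and it does not give the chance that a particular reported cluster is false.

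The matter is confined to one of three network measures under Secondary Aim B of a pilot study. The specific imaging hypothesis concerns Default Mode Network connectivity, and the clinical primary outcome is untouched. The change is worth making because it is cheap and does not require the unknown smoothness pattern to be settled.

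**What to change.** In the Amplitude measures paragraph, replace the random-field correction with permutation inference, family-wise corrected on maximum cluster size. Use for example 5,000 permutations, the number already set for the ICA test, and state that the maximum-cluster correction and sign-flipping are additions to what that section describes.

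- Change between two scans: flip the sign of each patient's between-scan difference map.
- Omnibus test over three scans: permute scans within patient.
- Group by time: permute group labels on the difference maps.
- Direction: test two-sided, or at 2.5% per direction, unless a direction for amplitude is fixed in advance.

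Sign-flipping assumes difference maps symmetric about zero under the null; the other two schemes assume exchangeability. Neither requires a smoothness model. Raising the cut to Z>3.1 while keeping the random-field correction is only a partial repair.

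The cost is plan wording and computing time, with no new data or visits. Where noise is smoother than the random-field model assumes, larger clusters will be needed for significance.

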### **Group analysis**

Our main goal in our analysis is to determine group-wise effects. The inter-subject variability however poses the main obstacle to gain meaningful effects. We will use our time-wise data to “subtract” measures between time points in the same individual, and analyze our data with repeated measure ANOVA (one factor is time point (intra-subject), other is group (inter-subject)).

Group comparison of the seed based correlation measures is straightforward, correlation values between the vmPFC and other DMN regions and subgenual cingulate will be used to detect any interaction between factors (time and group (responders and non-responders)).

The group analysis of ICA networks will be carried out by dual regression method, as it is presented on Figure 3. Individual network patterns will be obtained, and these individual patterns will be used in a second level analysis with SPM, where voxel based repeated measure ANOVA will be calculated. Similarly individual amplitude maps will be analyzed with SPM.

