## Rationale

Despite major advances in the treatment of mood disorders, depression remains a serious public health problem. In a recently published Sequenced Treatment Alternatives to Relieve Depression (STAR\*D) trial, patients had remission rates of 37%, 31%, 14% and 13% for four distinct types of pharmacotherapy treatment. Another limitation to pharmacological treatment is the delayed response, which can often take up to several weeks and is especially deleterious for suicidal patients. For these reasons, electroconvulsive therapy (ECT) represents an important and efficacious treatment modality for the treatment of depression. ECT generally provides faster amelioration of depressive symptoms and its efficacy is reported to be 65 to 85%. However, even with ECT some patients do not respond and the antidepressant response requires multiple sessions increasing risk of impaired cognitive function, which still remains the limiting factor in its use.

Ketamine is a non-barbiturate anesthetic that has been used infrequently as an anesthetic in ECT. As ketamine has no anticonvulsant properties as barbiturate anesthetics do, its use has been generally reserved for instances when a seizure cannot be elicited from a patient despite the application of maximum device settings. However, there are recent reports that demonstrate ketamine's favorable seizure and cognitive profile.

Furthermore, ketamine is hypothesized to possess intrinsic antidepressant properties when used as monotherapy for depression. Several investigators have determined that ketamine, at sub-anesthetic doses, alleviates depressive symptoms in animals. There is some recent evidence that the use of ketamine in ECT may enhance the overall outcome. A non-randomized trial by Okamoto shows a faster response when ECT is given with ketamine anesthesia compared to that with propofol. We propose a pilot study to measure both therapeutic efficacy and cognitive side effects of ECT using ketamine compared to methohexital in depressed patients.

Although electroconvulsive therapy (ECT), regardless of the anesthetic agent, is a highly effective form of treatment in major depression, very little is known about the underlying mechanism of action. Neuroimaging is a non-invasive technique which may provide more insight into the underlying changes in the neurophysiologic circuitry. Several PET investigations

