### **Secondary Aim B**

To use resting state and task related fMRI to identify ECT related functional network changes in the brain. Using resting state fMRI before and after ECT, we will (a) identify networks modulated by ECT (defined as a decrease or increase in functional connectivity from baseline to follow up scans), and we will (b) follow up their expression in the upcoming weeks, we will (c) identify functional networks of the brain which are correlated with superior clinical ECT outcome and we will (d) identify functional networks of the brain which are correlated with side effect profiles.

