### b. Assessment Instruments

The primary outcome measure is the HRSD-24 which will be administered at baseline and before each treatment. The HRSD-24 is a semistructured interview designed to rate the severity of depressive symptoms in patients with a primary depressive illness. We will use the 24-item version, which includes three items in addition to the original 21 (i.e., Helplessness, hopelessness, worthlessness).

Brief Psychiatric Rating Scale (BPRS) (Hillside Anchored version) BPRS will be administered at screening and after last ECT treatment.

Psychotic symptoms will be measured by the four item positive symptoms subscale (consisting of suspiciousness, hallucinations, unusual thought content, and conceptual disorganization) of the Brief Psychiatric Rating Scale (BPRS). After each ECT treatment BPRS+ will be administered as following: after full orientation recovery, two hours post ECT. If any of the items are positive (2 or higher) BPRS+ will be re administered at 4 hours post ECT. If symptoms persist, patients will be further evaluated by a study psychiatrist and will be treated clinically as needed. Of note, that as part of standard care, patients are under constant observation and monitoring after ECT until they are deemed stable to be discharged from the unit.

**Clinician-Administered Rating Scale for Mania (CARS-M):** The CARS-m is a brief, clinician-administered, semistructured interview, which rates presence versus absence of a symptom, its severity, and symptom change in response to treatment. It is used to characterize manic behavior, but also to capture psychotic symptoms. These items yield two subscale scores one for mania (items 1-100 and one for psychosis (items 11-15).

The secondary outcome measures are the scores of neuropsychological (NP) battery. The neuropsychological (NP) battery is administered to all subjects at baseline (prior to the first ECT), on ECT #4 and following the end of the acute phase of ECT. In addition the MMSE will be performed prior to each ECT session and assessment of postictal recovery of orientation after each ECT session.

The neuropsychological test battery consists of the following instruments:

- Reading subtest of the Wide Range Achievement Test, 3rd Edition (WRAT-3), which will only be administered at baseline
- Mini- Mental State Examination (MMSE)
- Postictal Recovery of Orientation
- Rey Auditory Verbal Learning Test (RAVLT)-Immediate

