### d. Outcome Criteria

## **1. Remitter criteria**

- (a)  $\geq 60\%$  decrease from baseline in HRSD total score, *and*
- (b) HRSD  $\leq 10$  on two consecutive ratings, *and*
- (c) HRSD does not change  $> 3$  points on last 2 consecutive treatments. We do not define a specific minimum or maximum number of ECT for a patient to be classified as a remitter.

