Since this is a pilot study, the goal is to estimate the magnitude of the effect sizes for use in designing a subsequent study. With 12 patients randomized to each of the two treatment groups, there is only 45% power with an alpha level of 5% to detect a difference of 50% remission rate in the methohexital group and an 80% remission rate in the ketamine group at visit 8. For the other aims, which look at the change in scores on various rating scales over time, there will be 80% power with an alpha level of 5% (2-sided) to detect a difference between the slopes (measuring rate of change in scores on tests per visit) for the two treatment groups of magnitude  $0.05\sigma$ , where  $\sigma$  is the standard deviation of scores in either treatment group at a single visit. If, for example, the standard deviation of the HRSD scores is 5.0, then there will be power to detect an increased rate of improvement in the ketamine group of 0.25 points per visit, corresponding to an average improvement of 2.0 more points per 8 visits in the ketamine group than whatever improvement is observed in the methohexital group (Diggle et al 1995).

Given the recognition that, with the small sample size, power will be low, the primary focus of analysis is to determine whether ECT with ketamine anesthesia compared to ECT with methohexital anesthesia produces a clinically significant effect, i.e., one that, even if it does not reach statistical significance, would justify a larger clinical trial to replicate effect size. We expect a mean number of 8 treatments to remission based on the results of a Consortium for Research in ECT paper.

Our specific hypothesis is that ECT will decrease functional connectivity in the Default Mode Network (time-wise hypothesis). We also think that the decrease in the expression of this network will correlate with the effectiveness of the ECT, or at least will show a difference

between responders and non-responders (group-wise hypothesis). In order to detect network changes, we will calculate seed based correlation, ICA network expressions and amplitude measures of the networks.

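### The hypothesised correlation between network change and ECT benefit has no written model; the only specified test, for the seed-based measures, uses an undefined responder split

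*Combined protocol and SAP*

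**What the plan says.** Secondary Aim B, item (c), sets out to "identify functional networks of the brain which are correlated with superior clinical ECT outcome". Section 13 (Data Analysis) turns this into a hypothesis: the fall in default-mode network expression "will correlate with the effectiveness of the ECT, or at least will show a difference" between responders and non-responders. The correlation comes first and the two-group difference is the fallback.

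The Group analysis section then proposes repeated-measures ANOVA, in which "one factor is time point (intra-subject), other is group (inter-subject". For the seed-based measures it names the groups: the correlation values "will be used to detect any interaction between factors (time and group (responders and non-responders". For the ICA and amplitude maps it does not say what the group factor is. The imaging parts of section 13 contain no regression or correlation of network change on HRSD.

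On the clinical side, "The primary outcome measure is the HRSD-24 which will be administered at baseline and before each treatment", and Table 2 adds a rating 24–72 hours after the last ECT. The outcome criteria in section 7d define remitters, partly by a "decrease from baseline in HRSD total score", and non-remitters. They do not define responders.

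**The concern.** The question posed is one of degree: does more network change go with more benefit? The one test written down asks whether two classes of patient differ. Splitting a score into two classes treats a patient just past the cut-off like one far past it, and the power lost is hard to spare in a pilot of this size.

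Two features make it worse. Because responder has no definition, the cut-off can be fixed after the scans have been seen. The non-responder cell is also likely to be very small. The Group analysis section calls group-wise effects its main goal and variability between subjects its main obstacle, and the pilot is meant to supply effect sizes for a larger trial. A contrast resting on a handful of non-responders is a weak basis for that.

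**Working it through.** **The plan's own figure.** The only imaging power statement is 80% with N=20 (Sample Size and Power). It comes from a cited fMRI paper on percent signal change. It cannot be reproduced, because no variances and no alpha are given, and it does not concern the responder comparison. No power or information figure is stated for that comparison.

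**Inputs**
- Share responding: the Rationale says of ECT that "its efficacy is reported to be 65 to 85" per cent. This is a literature figure and is not tied to any definition of response, so it is used here as an assumption.
- Sample: 24 patients are planned (Study Overview), and imaging-only patients may be added (section 3). N=20 is the number in Sample Size and Power. Both are shown.
- True correlation r between connectivity change and HRSD-24 change: not in the documents; assumed 0.3, 0.4 and 0.55.

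**Size of the smaller cell.** N × (1 − p):
- N=20: 20 × 0.35 = 7 down to 20 × 0.15 = 3 non-responders.
- N=24: 24 × 0.35 = 8.4 down to 24 × 0.15 = 3.6.

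**Information kept by the split.** For a normal score cut so that a share p falls in one class, and a linear association, the efficiency relative to the continuous score is φ(z_p)² / [p(1 − p)], where z_p is the normal quantile and φ the normal density.

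| p | φ(z_p)² | p(1 − p) | Efficiency | Loss |
|---|---|---|---|---|
| 0.50 | 0.1592 | 0.2500 | 0.637 | 36% |
| 0.65 | 0.1372 | 0.2275 | 0.603 | 40% |
| 0.80 | 0.0784 | 0.1600 | 0.490 | 51% |
| 0.85 | 0.0544 | 0.1275 | 0.426 | 57% |

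Over the cited 65–85% the loss is 40–57%. In effective patients, 20 become 20 × 0.603 = 12.1 down to 20 × 0.426 = 8.5. The 36% loss is the minimum under this model and needs equal halves, which lies outside the cited range.

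**Power.** Simulated bivariate normal data, two-sided 5%, 65:35 split. The correlation test is compared with a two-sample t test on within-patient change, which is what a time-by-group interaction reduces to with two time points. Repeat runs move these figures by up to about one point.

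| r (assumed) | N=20: continuous v split | N=24: continuous v split |
|---|---|---|
| 0.30 | 25% v 17% | 30% v 19% |
| 0.40 | 43% v 27% | 51% v 32% |
| 0.55 | 75% v 49% | 83% v 57% |

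**If outcomes cluster.** Suppose 65% of patients have a mean HRSD reduction of 78% (SD 8) and 35% a mean of 30% (SD 15). These values are illustrative. The variance between clusters is 0.65 × 0.35 × 48² = 524.2. The variance within them is 0.65 × 64 + 0.35 × 225 = 120.4. A split by cluster keeps 524.2 / 644.6 = 0.81, a loss of about 19%. A cut at 60% reduction gives about 18% by simulation. At N=20 and r=0.55, power is then about 75% v 65%.

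**The case against.** A reader might infer that the plan abandoned the continuous question and chose to discard data. The documents do not support that. Section 13 states that "the decrease in the expression of this network will correlate with the effectiveness of the ECT", and the group-wise label there closes a sentence containing both the correlation and the two-group difference. The fault is that the correlation was hypothesised and never given a model.

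A reader might also take a single loss figure as a fact about this trial. It is not. It needs a roughly normal HRSD-24 change, a linear association and a responder share, none of which the documents supply. Normality is doubtful: treatment ends at remission, while non-remitters continue for at least 10 treatments to a plateau, so end scores may cluster. The worked example shows the loss could be about half the lower end of the 40–57% range. If network change differed only by class, with no gradient within classes, a correctly placed split would not be inferior.

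Nor does the point reach all the imaging work. The responder factor is written only for the seed-based measures. Sample Size and Power gives change across time points as the imaging objective, and that analysis does not use the split.

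Finally, this is a secondary aim of a pilot, and at r=0.3 neither analysis has useful power. All of this limits the size and scope of the point. It does not defend an undefined split as the only written test of a correlation hypothesis.

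**Conclusion.** The point holds, with a conditional size. The aim and the hypothesis call for a correlation, and the only specified test is a responder by time interaction for the seed-based measures, with responder undefined. With a roughly normal HRSD-24 change, a linear association and 65–85% responding, the split gives up about 40–57% of the information. With clustered outcomes the loss is nearer 20%. The continuous score had the higher power in every scenario computed here, but the gain depends on the assumed r and is small in absolute terms when r is low. The lack of a definition, and so of a pre-set cut-off, holds whatever the distribution.

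**What to change.** In Group analysis, make the test of network change against clinical benefit a regression of within-patient change in connectivity on end-of-course HRSD-24, with baseline HRSD-24 as a covariate. Using HRSD-24 change with baseline as a covariate gives the same test. Name the pair of scans that defines the change. Avoid percent change: section 3 lets imaging-only patients enter with low Hamilton scores, and percentages on a low baseline are unstable. If the ICA and amplitude maps are also to be related to outcome, use the same covariate and say so.

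Show remitters against non-remitters as a description only. First reconcile the remission definitions: the Primary outcome section uses scores below 10, the Study Overview uses 10 or below, and the Remitter criteria add a fall of at least 60%.

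The cost is a short revision of the analysis text, with no new data from the randomised patients. Linearity and influential patients must be checked, which matters with 20 to 24 points. The sponsor should also confirm that imaging-only patients have HRSD-24 ratings at baseline and at the end of the course.
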